1 ADMINISTRATIVE INFORMATION

1.1 Trial Name

1.1.1 Trial Registration

ClinicalTrials.gov Identifier: NCT01793129

1.2 Protocol Version

Version 3.0

1.3 SAP Revision History

Ver.	Justification for change	Date
0.1	Initial Version	2021-05-3
0.2	2 nd draft	2021-10-05
0.3	3 rd draft	2021-12-03
0.4	4 th draft	2022-06-13
0.6	6 th draft	2022-09-13
0.7	7 th draft	2022-10-18
1.0	Approved	2022-11-02
1.1	Per study subcommittee deliberation over email on March 3 rd and 4 th , 2023, changed the model used for analysis of ordinal outcomes from a proportional odds model to a set of logistic regression models with post processing to facilitate calculations of relative risks and/or risk differences. This change made the analysis more consistent with the analysis of previous hypothermia trials.	2023-01-02

1.4 List of Abbreviations

Abbreviation:	Definition:
AE	Adverse event
BPD	Bronchopulmonary dysplasia
DCC	Data Coordinating Center
DSMB	Data and safety monitoring board
FAS	Full analysis set
FU	Preemie Hypothermia Follow-up database
GA	Gestational age
HIE	Hypoxic-ischemic encephalopathy
ICH	Intracranial hemorrhage
hr	Hours
SC	Steering committee
IRB	Institutional Review Board
ITT	Intent-to-treat
IVH	Intraventricular hemorrhage
mITT	Modified Intent-to-treat
N/A	Not Applicable
NE	Neonatal encephalopathy
NICHD	National Institute of Child Health and Human Development
NIH	National Institute of Health
PP	Per Protocol
RS	Research site
SAE	Severe adverse event
SAP	Statistical analysis plan
Tes	Temperature per esophageal probe
wks	Weeks

2 INTRODUCTION

The Preemie Hypothermia Trial was a randomized multicenter trial conducted to determine whether whole body hypothermia for 72 hrs in preterm infants 33-35 wks gestational age (GA) and ≥ 1500 grams birth weight who present at <6 hrs postnatal age with moderate to severe neonatal encephalopathy (NE) formerly called hypoxic-ischemic encephalopathy (HIE) is safe and will reduce death or moderate/severe disability at 18-22 months corrected age.

2.1 Background and Rationale

Most clinical studies of NE and potential interventions have targeted infants ≥ 36 wks GA. Although many interventions have been suggested and assessed for prevention or palliation of NE in high-income countries, the only one currently supported by rigorous clinical evidence to improve outcome in human newborns has been hypothermia (targeting core temperature of 33.5 with a range of 33.0 to 34.0°C. - with or without head cooling) implemented at ≤ 6 hrs of postnatal age and maintained for 72 hrs in infants ≥ 36 wks GA with moderate or severe NE. Translation of these findings to infants who are more premature has been suggested as a subject for further scrutiny by some and actually implemented by others.

Reports of induced hypothermia include infants of lower GA, but the incidence of such infants and their outcomes are unclear. The protocol lists several reported studies and verbally reported cases where hypothermia treatment was used at GAs less than 36 wks. These cases are occurring even though the literature lacks the evidence to support hypothermia treatment at GA < 36 wks. Concern about increased frequency or severity of adverse events or other problems in infants 33-35 wks GA subjected to 'therapeutic' hypothermia is real, but there are minimal human data to determine whether benefits will outweigh risks. Given the ongoing use of induced hypothermia for indications that are not evidence-based (including use at <36 wks GA) and the unknown risk-benefit ratios, it was deemed important to complete this trial as designed to systematically generate prospective data and analyze the data in a rigorous manner.

2.2 Study Objectives

2.2.1 Study Hypotheses

The risk of death or moderate or severe disability at 18-22 months corrected age will be decreased in infants 33 0/7 - 35 6/7 wks GA and ≥ 1500 grams birth weight with moderate or severe NE due to presumed perinatal hypoxia-ischemia at < 6 hours age who undergo targeted temperature management with whole body hypothermia to 33.5°C (as monitored by esophageal temperature [Tes]) for 72 hours than in those with core temperature (also per Tes) targeted at 37.0°C (controls).

Primary objectives

- 1) To assess differences in death or moderate/severe disability at 18-22 months in enrolled infants randomized to whole body hypothermia for 72 hours, compared to those randomized to normothermia for 72 hours.
- 2) To determine short-term safety (i.e., within 108 hours of baseline [time of insertion of esophageal probe]) of targeted temperature management with whole body hypothermia for 72 hours in infants 33 0/7 -35 6/7 weeks GA with moderate or severe NE at ≤ 6 hours of age. Safety criteria will include serious adverse effects (SAEs): intracranial hemorrhage, cardiac arrhythmia; persistent acidosis;

thrombosis; bleeding; skin changes; necrotizing enterocolitis (NEC); spontaneous intestinal perforation (SIP); esophageal perforation attributable to the placement of the esophageal tube, ulceration or bleeding from the esophageal probe; hypo- and hyperglycemia; receipt of ECMO; thrombocytopenia, and death.

Secondary objectives

To assess differences between study groups with respect to a select set of secondary efficacy and safety outcomes which are listed in Sections 6.2 and 6.3.

3 STUDY METHODS

This statistical analysis plan (SAP) contains detailed information about statistical analysis to be performed to assess the above mentioned primary and secondary objectives once the final Preemie Hypothermia analysis datasets are constructed.

3.1 Trial design

The trial was a staged prospective, randomized multicenter trial with qualifying infants 33 0/7 -35 6/7 weeks GA to be randomized to whole body hypothermia (33.5 °C esophageal temperature [Tes]) for 72 hours or normothermia (with steps incorporated to avoid hyperthermia [$>37.3^{\circ}\text{C}$ Tes]). The treatment assignment was unmasked. The “staged” component of the trial refers to how the original trial design included an assessment of enrollment after 2 years of enrollment. If enrollment was sufficient during the first 2 years, then the study would continue to enroll until completion unless the DSMB deemed it necessary to stop the study at any DSMB assessment.

3.2 Study Intervention and Process

Infants were randomized within 6 hours of age to either whole body cooling or normothermia for 72 hours. The targeted temperature management for the whole body cooling group included a targeted temperature of Tes 33.5°C, (acceptable Tes 33.0 – 34.0°C); the targeted temperature management for normothermia included a targeted temperature range of Tes 36.5 – 37.3°C, with steps to prevent Tes $>37.3^{\circ}\text{C}$). In both groups the treatment period was 72 hours. Hypothermia is attained and maintained with the Cincinnati Sub-Zero Hyper/Hypothermia Device. Surveillance for safety and adverse events within 108 hours of baseline (insertion of esophageal probe) is conducted. This includes cranial ultrasound no later than 24 hours after baseline read by local center readers. All survivors undergo brain MRI after the intervention at 10-17 days of age, with strong encouragement to obtain the MRI after the intervention or prior to NICU discharge/transfer to non-NRN center (if <10 -17 days of postnatal age). MRI studies obtained at other times post-hypothermia/control intervention are included as well, and all enrolled babies undergo standard interdisciplinary neurodevelopmental assessment at 18-22 months corrected age (although the Covid pandemic occasionally required deferral of this visit, in which case the visit was scheduled as early as possible once follow-up visits were possible).

3.3 Randomization

After informed consent was obtained, qualifying infants were randomized by 6 hours of age to either hypothermia or the non-cooled control group. Randomization occurred 24 hours a day, 7 days a week through the Data Coordinating Center at RTI International, Research Triangle Park, NC. Infants were stratified by center and degree of NE (moderate versus severe). In the unlikely event of a multiple gestation qualifying for inclusion, all who qualified were randomized independently.

3.4 Sample Size

During the design phase, the potential number of eligible subjects was uncertain due to limited and variable data such that traditional sample size determination was not likely to be helpful. The original NRN hypothermia trial in infants ≥ 36 weeks GA found a frequency of 62% death or moderate/severe disability in control infants; there were no data regarding the incidence of death or disability after NE at the targeted gestational age of this study during the design phase of this trial. Given increased fragility associated with this degree of prematurity, it seemed likely that the incidence of death or moderate/severe disability in the control arm was likely to be at least 70%.

To achieve 80% power to detect a decrease in death or moderate/severe disability from 70 to 50% a sample size of about 110 subjects per arm is needed. A decrease from 70 to 55% would also be clinically significant but would require about 190 subjects per arm. These sample size requirements were deemed unfeasible for the population involved in this research, so the Premie Hypothermia study was designed to randomize 168 babies and analyze the data using a Bayesian approach to estimate the effect of hypothermia relative to normothermia with as much precision as possible and allow for the calculation of a probability of treatment benefit for hypothermia. The 168 was derived from projected ability to enroll among participating sites and experience from the previous Late Hypothermia trial. This trial was not powered in the traditional sense, but simulations under specified scenarios were run and the results showed that the trial design had more than a 75% chance of observing a final posterior probability of at least 0.80 for $RR < 1$ (indicating treatment benefit) given the data, when the true RR is close to 0.70.

3.5 Analysis Structure

The main goal of this analysis is to evaluate whether preemie infants 33-35 weeks GA with moderate to severe NE at ≤ 6 hrs age targeted to a core temperature of 33.5°C (as monitored by esophageal temperature) for 72 hours in the hypothermia arm versus core temperature targeted to 37.0°C reduces the risk of death or moderate or severe disability at 18-22 months corrected age. Secondary goals of analysis will be completed to more fully understand the effect of hypothermia on components of the primary outcome, as well as safety outcomes.

3.6 Statistical Interim Analysis and Stopping Guidance

Interim statistical analyses and stopping guidance are given in sections 4.3 – 4.6 of protocol, summarized in Table 1 of protocol.

3.7 Timing of Interim and Final Analysis

Final analyses were planned to occur after 168 infants were consented, enrolled, randomized, and followed to 18-22 months corrected age. The study analysis database is constructed using those who died before the 18-22 month follow-up and all survivors not lost to follow-up who underwent protocol-specified neurodevelopmental assessment.

4 STATISTICAL PRINCIPLES

The Premie Hypothermia trial has a Bayesian design with Bayesian interim analyses of safety and efficacy. Interim analyses of safety and efficacy were completed as described in the protocol.

4.1 Modeling Processes, Prior Specification, and Reporting Procedures

- For binary outcomes, the protocol specified that a Bayesian log-binomial regression model with random center effect would be fit to estimate the relative risk of hypothermia relative to normothermia. However, since the protocol was written, an increasing emphasis has been placed on including inference on risk differences in clinical trial reports, so a logistic regression model with random center effect will be fit followed by post-processing of individual predicted probabilities of outcome to estimate posteriors of relative risk and risk differences.¹
 - Weakly informative priors will be used during analyses to better understand the effect of hypothermia on outcomes considered in this trial:
 - On the relative risk and risk difference scales of primary outcome and components, the priors for the treatment effect will include a skeptical prior, a neutral prior, and an enthusiastic prior. For all other outcomes, only the neutral prior will be used.
 - For the intercept and the encephalopathy terms, broad neutral priors will be used.
 - For the random center effect, a Normal prior centered at 0 will be used where the standard deviation parameter of this prior will have a half-normal hyperprior with mean equal to 0 and standard deviation equal to 1.
 - Further details about these priors are given in section 6.4.2 and 6.4.3
 - Posterior distributions, posterior means, posterior probabilities of benefit, and 95% credible intervals will be reported for the effect of hypothermia on the outcomes considered.
- For count outcomes such as days or durations, a negative binomial model with random center effect will be fit to estimate relative risk.
 - Weakly informative priors will be used during analyses to better understand the effect of hypothermia on outcomes considered in this trial:
 - On the relative risk scale, the priors for the treatment effect will include a neutral prior.
 - For the intercept and the encephalopathy terms, broad neutral priors will be used.
 - For the random center effect, a Normal prior centered at 0 will be used where the standard deviation parameter of this prior will have a half-normal hyperprior with mean equal to 0 and standard deviation equal to 1.
 - Further details about these priors are given in section 6.4.2 and 6.4.3

¹ Andrew Gelman and Iain Pardoe. Average Predictive Comparisons for Models with Nonlinearity, interactions, and variance components. *Sociological Methodology*. May 18, 2007.

- Posterior distributions, posterior means, posterior probabilities of benefit, and 95% credible intervals will be reported for the effect of hypothermia on the outcomes considered.

4.2 Protocol violations/Deviations

Protocol violations (PV) and minor protocol deviations (MPD) were collected using a specified set of descriptions. Possible reasons for PV and MPD were:

- Study intervention never started
- Wrong treatment intervention applied
- Infant ineligible
- No consent
- Neuro exam not done
- Wrong stratification variables used at randomization
- Too early removal of esophageal probe
- Infant randomized after 6 hours
- Intervention initiated after 6 hours and 30 minutes
- Intervention discontinued early
- Equipment malfunction
- Cranial ultrasound completed outside of protocol-specified age window
- Tepid sponge bath not provided
- Infant not rewarmed per protocol
- Other violation

PVs and MPDs will be descriptively summarized in terms of infants per arm with any PV(MPD) and in terms of number of PV(MPD) per arm.

4.3 Analysis Datasets

This analysis will use two analysis populations, a full analysis set (FAS) and per-protocol (PP).² The FAS analysis population will include all randomized infants with ascertained primary outcomes. This FAS analysis population is recognized as being as close as possible to an intent-to-treat population. All analyses based on the FAS will analyze infants as randomized. The PP analysis population will include all infants who received their randomized treatment (72 hours of hypothermia or normothermia) and have a determined primary outcome. All analyses based on the PP will analyze infants as treated.

² ICH E9: <https://www.fda.gov/regulatory-information/search-fda-guidance-documents/e9-statistical-principles-clinical-trials>

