6 STATISTICAL ANALYSIS

6.1 Primary Efficacy Outcome

The primary outcome will be death or moderate to severe disability at 18-22 months corrected age (or later as required by Covid pandemic) (*Binary*).³ Death will be identified by finding an indication of death on the PH13 network status form, PH15 adverse event form, DEATH_FU and DEATH_NEW variables from the follow-up (FU) analysis dataset, JFSTATUS = 3 from the FU analysis dataset.⁴

The presence or absence of disability will be determined by the standard NRN interdisciplinary follow-up exam. Where possible, the primary outcome values will be taken from the FU analysis dataset. Binary variables for severe, moderate, mild, and no disability will be created using the following criteria. A single binary moderate or severe disability variable will be created from this individual disability severity variable to identify infants with moderate or severe disability (= 1, if severe disability or moderate disability is indicated; = 0, if disability can be determined and not equal to severe or moderate.)

Severe disability will be defined by the presence of any of the following:

- a Bayley III cognitive score < 70 (*FU: B3_COG70*),
- Gross Motor Functional Classification Status (GMFCS) Level of 3-5 (*FU:GMF_LEV >= 3*),
 - Note: The GMF_LEV variable will need to be programmed in accordance with GMF_LEV as programmed in the regular RTI FU (follow-up) analysis dataset.
- blindness (visual acuity $< 20/200$ in the both eyes as determined by an ophthalmologist) (*FU: VISIONR and FU:VISIONL equal to 4 or 5, B.1.e*) or
- profound hearing loss (inability to understand commands despite placement of a cochlear implant or amplification) (*FU:HEARIMP = 1 (B.2.b) and FU:HEARAID = 1, 2, or 3 (B.2.b.1) and FU:HEARCOC = 1, 2, or 3 (B.2.b.2)*).

Moderate disability will be defined by:

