- Posterior plot of treatment effect
- Posterior median and posterior standard deviation
- 95% credible interval
- For relative risk, posterior probabilities of >0%, >5%, >10%, and >20% decrease in the primary outcome will be calculated
- For risk difference, posterior probabilities of >0%, >1%, >2%, >3%, and >5% decrease in primary outcome will be calculated
- forest plot of the center level effect and 95% credible intervals.

If the FAS analysis of the primary outcome results in any clinically notable findings, then the primary outcome may also be analyzed in an exploratory fashion using the PP population.

Analysis of Secondary Outcomes

With respect to secondary outcomes, analyses will follow the same process as the primary outcome analysis defined above. See MockTablesAppendix.docx for list of selected variables.

Analysis of Safety (AE) and Hospital Outcomes

Safety and hospital outcomes listed in Sections 6.2 and 6.3 will be analyzed using the FAS population and if necessary, the PP population using relative risk models, proportional odds models, or Negative Binomial models, depending on the type of outcome.

With respect to binary safety outcomes, the estimated posterior distribution of relative risk, θ , based on the data and the neutral prior will be used to determine posterior probabilities of harm from the intervention, $\Pr(\theta > 1 | X)$, as well as 95% credible intervals.

For ordinal safety outcomes, the estimated posterior distribution odds ratio for the cumulative logits, ϕ , will be estimated based on the data and the neutral prior. In addition, posterior probabilities of harm, $\Pr(\phi > 1 | X)$, and 95% credible intervals of ϕ will be calculated.

For count type safety outcome, the estimated posterior distribution of the treatment mean rate, ϕ , will be estimated based on the data and the neutral prior. In addition, posterior probabilities of harm, $\Pr(\phi > 1 | X)$, and 95% credible intervals of ϕ will be calculated.

Analysis of Ultrasound, CT scan, MRI and encephalopathy outcomes

Ultrasound, CT scan, MRI, and encephalopathy outcomes will be analyzed using the FAS population. Head ultrasounds, CT scans, and brain MRIs will be summarized by treatment and time (prior to intervention, during intervention, after intervention, any time). Summaries will be created for number of babies with any abnormal findings during time period data recorded, and for total events across all babies during any time period.

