6.5.7 Sensitivity Analysis

In addition to adjusting for level of encephalopathy and center as a random effect, sensitivity analyses may be completed, at the discretion of the Preemie Hypothermia subcommittee, by selecting baseline covariates that differ across the two treatments. These covariates will be selected from those covariates listed in section 5.3. This analysis will only be completed for the primary outcome (death or moderate to severe disability at 18-22 months corrected age) and Death. These sensitivity analyses will be based on the FAS population.

In addition to the FAS population-based analysis, exploratory PP analyses may be done using the PP population on the primary or secondary outcomes at the discretion of the Preemie Hypothermia subcommittee, if the FAS analysis of the primary or secondary outcome results in any clinically notable findings.

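### As worded, the per-protocol set drops infants who die on assigned treatment before 72 hours, so the exploratory PP estimate is conditioned on the outcome

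*SAP*

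**What the plan says.** SAP Section 4.3 sets out two populations.

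- **FAS:** "The FAS analysis population will include all randomized infants with ascertained primary outcomes", analysed as randomized.
- **PP:** infants who "received their randomized treatment (72 hours of hypothermia or normothermia) and have a determined primary outcome". The section adds: "All analyses based on the PP will analyze infants as treated".

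Three other places bear on how the PP definition works.

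- Section 3.2: "In both groups the treatment period was 72 hours".
- Section 6.1: "The primary outcome will be death or moderate to severe disability at 18-22 months corrected age". No minimum survival time is attached to death.
- Section 4.2 lists "Intervention discontinued early" among the reasons for a violation or deviation, without separating treatment that ended because the infant died.

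The PP analysis is conditional. Section 6.5.5 allows it as an exploratory option under this condition: "If the FAS analysis of the primary outcome results in any clinically notable findings". Section 6.5.7 extends this to secondary outcomes, at the subcommittee's discretion, "if the FAS analysis of the primary or secondary outcome results in any clinically notable findings". No threshold for a clinically notable finding is given. For safety and hospital outcomes, Section 6.5.5 uses a different condition, which is simply that the PP analysis be necessary.

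**The concern.** An infant who dies at, say, 40 hours while on the assigned treatment has a determined primary outcome. That infant did not receive 72 hours of treatment, so fails the treatment condition for the PP set. Death is what ended the treatment, and death is part of the endpoint. Membership of the PP set then depends on the outcome being analysed, and only events, never non-events, are removed by this route.

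At stake is how far an exploratory PP estimate can be trusted. Removing early deaths lowers the event risk in both arms. It changes the relative risk whenever the arms differ in early deaths or in overall risk. If a PP result were reported beside the FAS result, readers would be comparing two estimates that differ partly because of this rule and not because of adherence.

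**Working it through.** **Reading the definitions together.** For an infant who dies on assigned treatment before 72 hours:

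| Condition | Source in SAP | Met? |
|---|---|---|
| Randomized with an ascertained outcome (FAS) | 4.3 | Yes |
| Primary outcome determined (PP) | 4.3, 6.1 | Yes, an event |
| 72 hours of assigned treatment received (PP) | 4.3, 3.2 | No |

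The infant is in the FAS and, on the plain wording, outside the PP set. Analysing PP infants as treated does not bring the infant back, because that rule applies only to infants already in the set.

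**Size.** The SAP states no figure to reproduce, so this is an illustration.

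Inputs:
- Risks of 70% (control) and 50% (hypothermia): planning figures in Section 3.4.
- 168 infants: Section 3.4. Taken as 84 per arm, which is an assumption.
- Share *d* of an arm dying before 72 hours: not given in the SAP. Assumed, with a range shown.
- No other PP exclusions: assumed, to isolate this rule.

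Formula: if a share *d* of an arm with true risk *p* dies early, PP risk = (*p* − *d*)/(1 − *d*).

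*True benefit, 70% v 50%, FAS RR = 0.50/0.70 = 0.714, equal early deaths.* The denominators cancel, so PP RR = (0.50 − *d*)/(0.70 − *d*):

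| *d*, each arm | PP risk, control | PP risk, hypothermia | PP RR |
|---|---|---|---|
| 5% | 0.65/0.95 = 0.684 | 0.45/0.95 = 0.474 | 0.692 |
| 10% | 0.60/0.90 = 0.667 | 0.40/0.90 = 0.444 | 0.667 |
| 20% | 0.50/0.80 = 0.625 | 0.30/0.80 = 0.375 | 0.600 |

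At 10%, 0.10 × 84 = 8.4 infants per arm are lost. They are 0.10/0.70 = 14% of control events and 0.10/0.50 = 20% of hypothermia events. The risk difference moves from −20.0 to −22.2 points.

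*No true effect, 70% v 70%, FAS RR = 1.00:*

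| Early deaths, hypothermia v control | PP RR |
|---|---|
| 10% v 10% | 0.667/0.667 = 1.00 |
| 10% v 5% | (0.60/0.90)/(0.65/0.95) = 0.667/0.684 = 0.974 |
| 5% v 10% | 0.684/0.667 = 1.026 |
| 15% v 5% | (0.55/0.85)/(0.65/0.95) = 0.647/0.684 = 0.946 |
| 5% v 15% | 0.684/0.647 = 1.057 |

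With equal overall risk, the PP estimate favours the arm with more early deaths. The distortion grows as overall risk falls. At 62% in both arms, the control rate that Section 3.4 quotes from the earlier trial in more mature infants, 10% v 5% gives (0.52/0.90)/(0.57/0.95) = 0.578/0.600 = 0.963.

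**With early deaths kept in** and nobody else excluded, the PP set equals the FAS and the RR returns to 0.714.

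**The case against.** **The parenthesis may only name the regimen.** Elsewhere the SAP uses 72 hours as a label for the assigned treatment, and it never says outright that early deaths are removed. This reading is possible. But nothing else in the SAP supports keeping these infants, and two programmers could build different PP sets from the same sentence. The wording needs settling on either reading.

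**Nothing confirmatory rests on the PP set.** This stands. Section 6.5.5 lists six analyses of the primary outcome, all on the FAS. PP is optional and exploratory. A reader might infer that PP is there to corroborate the FAS result, but the SAP does not give it that role.

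**Early mortality is not hidden.** A reader might infer that a change in early deaths would disappear from view. The SAP does not support that. The FAS keeps every death with an ascertained outcome. Death is a secondary outcome (6.4), and components of the primary outcome are analysed under all three priors (6.5.3, 6.5.5). Death before discharge is a hospital outcome (6.3), and deaths are counted in the CONSORT diagram (6.5.1).

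**The trigger is disclosed.** A reader might infer that running PP only after a notable FAS result adds a further bias to the PP estimate. The SAP announces the condition in advance, and its wording could cover harm as well as benefit. Selecting on a favourable FAS result also shifts the FAS estimate in the selected trials, so the shift is not specific to PP. What stands is that clinically notable is undefined in a trial whose treatment was unmasked (3.1). That is a lesser point and largely one of preference.

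**Conclusion.** The PP definition is wrong as written, with limited consequence. On its plain wording it removes primary-outcome events because they occurred, so the exploratory PP estimate is conditioned on the outcome. With a true benefit at the planning rates, equal early deaths of 5% to 20% per arm move the RR from 0.714 to between 0.69 and 0.60, which exaggerates the benefit. With no true effect at 70%, a five-point imbalance in early deaths moves the RR by about 0.03 in either direction, and balanced early deaths produce no bias.

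These sizes rest on assumed early-death shares, equal arms and no other PP exclusions. They do not predict the trial's result. The primary FAS conclusion and the mortality analyses do not change.

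**What to change.** Add one sentence to SAP Section 4.3: infants who received their assigned temperature management until death before 72 hours remain in the PP set. This is a rule for the analysis set only and changes nothing in how infants are treated. It costs one sentence and one condition in the program that builds the set.

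Optional and secondary: in Sections 6.5.5 and 6.5.7, either run the exploratory PP analysis of the primary outcome whatever the FAS shows, or define a clinically notable finding before results by arm are seen. The first costs one more run of an existing model and the second costs a sentence.
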